# Sensitivity Analyses

To evaluate the robustness of the findings of the primary outcome analysis, the following sensitivity analyses will be performed:

- Per-protocol analysis: estimating treatment effects among participants who completed their allocated therapy (i.e., participants who completed all 16 therapy sessions or participants who met criteria for early completiona).
- Multiple imputation sensitivity analysis: compare primary model with only assessment completers to model with missing outcome data imputed to examine if data is missing at random (MAR). Missing data in the outcome variable will be handled using multiple imputation via chained equations.

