#### Study Design

This study is a pragmatic, single-blind multicentre superiority randomized controlled trial with four arms: CR, PE, EMDR, and WL. Therapy in all three active arms will be delivered over 16 sessions by trained therapists working in routine mental health services. All groups receive TAU for psychosis and will be assessed at T0, T2, T3, T6. Participants in the WL condition receive therapy of choice after T6.

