# Safety Analysis

During study participation, trial therapists were asked to monitor and report any severe adverse events (e.g., death, life threatening situations) and their possible study-relatedness. Severe adverse events will be summarized over the full study period (i.e., baseline up until 6-month follow-up) and reported by treatment arm.

In addition, all participants were asked to monitor adversities and revictimization weekly using smartphone questionnaires up to the 6-month assessment timepoint to enhance ecological validity. To assess group differences on these tertiary outcomes, events reported in the weekly online questionnaires will be aggregated between assessment timepoints and averaged to generate a single composite score corresponding to each formal assessment timepoint (i.e. baseline, T2, T3, and T6) for LMM-analysis.

<sup>a Early completion of EMDR or PE therapy was permitted only after consultation with the therapist and supervisor, and required that all trauma memories on the case conceptualization achieved Subjective Units of Distress (SUDs) scores of 0, participants scored 0 on both the re-experiencing (section B) and avoidance (section C) sections of the PCL-5, all psychosis targets achieved SUD scores of 0, and psychosis symptoms were in remission.

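### The per-protocol set keeps short-course PE and EMDR participants only if they are near remission, has no such route for CR and does not place WL, so it is a weak robustness check.

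*SAP*

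**What the plan says.** Under Sensitivity Analyses, the SAP lists analyses whose purpose is "To evaluate the robustness of the findings of the primary outcome analysis". The first is a per-protocol analysis, "estimating treatment effects among participants who completed their allocated therapy", and it defines these as "participants who completed all 16 therapy sessions or participants who met criteria for early completion".

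Footnote a, attached to that definition and printed below the Safety Analysis text, supplies the criteria: "Early completion of EMDR or PE therapy was permitted only after consultation with the therapist and supervisor". It then sets these conditions, all of which must be met:

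- a SUD rating of 0 for every trauma memory in the case conceptualization;
- on PTSD symptoms, "participants scored 0 on both the re-experiencing (section B) and avoidance (section C) sections of the PCL-5";
- a SUD rating of 0 for every psychosis target, together with remission of psychosis.

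CR is not named in the footnote, although Study Design plans 16 sessions for all three therapies. For the control arm, Study Design says "Participants in the WL condition receive therapy of choice after T6". T6 is the last assessment. Primary Outcome Analysis makes WL the reference group of the model. Table 1 lists the PCL-5 as a trial outcome, the self-reported counterpart of the researcher-rated CAPS-5.

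**The concern.** Membership of an analysis set should not depend on how well the participant did. Here, for anyone in PE or EMDR who stopped before session 16, it does. The criterion is measured after randomisation and includes PTSD symptom scores that stand close to the primary outcome. Adjusting for baseline CAPS-5 does not remove that selection.

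The rule also differs by arm. PE and EMDR have a symptom-based way in, CR has none, and WL has no therapy to complete during follow-up. Three therapy v WL estimates that will be read side by side would rest on differently selected sets.

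What is at stake is interpretation. If the per-protocol estimate agrees with ITT, it will be reported as support for the primary result, yet the agreement could partly reflect who was left in the set.

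**Working it through.** The SAP gives no figure for this analysis set: no expected stopping rate, early-completion rate or set size. Its sample size of 50 per arm is not touched by this point. The check is a reading by arm, followed by an illustration.

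**Who enters, by arm**

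| Arm | All 16 sessions | Fewer than 16, criteria met | Fewer than 16, criteria not met |
|---|---|---|---|
| PE, EMDR | in | in | out |
| CR | in | no criteria given, so out | out |
| WL | not applicable | not applicable | not applicable |

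**Direction.** Let p be the fraction of an arm removed, and m_k and m_r the mean outcomes of those kept and removed. The full-arm mean is (1−p)m_k + p·m_r, so the shift caused by selection is m_k − [(1−p)m_k + p·m_r] = p(m_k − m_r). The arm looks better than it is if those removed did worse than those kept. In PE and EMDR, those removed are the short-course participants who did not meet the criteria, so this is the likely case. It is not guaranteed, because it also depends on why people stopped.

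**Illustrative size for PE and EMDR v WL.** These assumptions are not in the SAP: no true effect, all WL kept, outcome standardised with lower values better, and a fraction s stopping short independently of outcome. A fraction q meets the criteria, taken as the lowest q of an index with correlation r to the outcome. With φ(z_q) the standard normal density at the q-quantile:

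shift = −s·r·φ(z_q) / (1 − s + s·q)

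- Low end, s = 0.2, r = 0.5, q = 0.1, φ = 0.1755: 0.2 × 0.5 × 0.1755 / 0.82 = 0.021 SD in favour of therapy.
- High end, s = 0.4, r = 0.7, q = 0.3, φ = 0.3477: 0.4 × 0.7 × 0.3477 / 0.72 = 0.135 SD in favour of therapy.

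Simulation over s = 0.2, 0.3, 0.4, q = 0.1, 0.2, 0.3 and r = 0.5, 0.7 gave 0.021 to 0.136 SD, which agrees. CR shifts by 0 under these assumptions. With 50 per arm, the low end means 10 stop short and 1 of them is kept. The high end means 20 stop short and 6 are kept.

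**If few meet the criteria.** With q = 0.05 (φ = 0.1031) and r = 0.6, s = 0.2 gives 0.2 × 0.6 × 0.1031 / 0.81 = 0.015 SD, and s = 0.4 gives 0.4 × 0.6 × 0.1031 / 0.62 = 0.040 SD.

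**CR v WL.** Suppose a fraction e of CR participants who meet the same criteria also stop early and are excluded, while s = 0.2 of the others stop short. The shift is r·φ(z_q)(e − s) / [(1 − e)q + (1 − s)(1 − q)], against therapy.

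- Low end, e = 0.5, q = 0.1, r = 0.5: 0.5 × 0.1755 × 0.3 / 0.77 = 0.034 SD (simulated 0.035).
- High end, e = 1, q = 0.3, r = 0.7: 0.7 × 0.3477 × 0.8 / 0.56 = 0.348 SD (simulated 0.347).

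If recovered CR participants continue to session 16, this shift shrinks or disappears.

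**The case against.** The strongest reply is that a participant who met pre-set completion criteria did follow the protocol. Dropping such people would remove the fastest responders and bias against therapy. The rule also drops short-course participants who improved but missed one strict condition. This stands in part: the net direction depends on why others stopped, so a reader should not infer that the bias towards PE and EMDR holds by construction. It does not make the set a sound one, since retention of short-course participants still depends on symptoms.

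Several stronger readings are not supported:

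- *That no WL participant qualifies, so no contrast can be estimated.* WL is the model's reference group, and keeping all of it is the sensible reading. What is missing is the sentence that says so.
- *That the comparison of PE or EMDR with CR is biased.* The objectives and post-hoc comparisons set each therapy against WL. No therapy v therapy contrast is planned, and the reason CR has no early-completion route may lie in the protocol.
- *That those kept are symptom-free.* The footnote names PCL-5 sections B and C, not D and E. Selection is on PCL-5, SUDs and psychosis status, not on CAPS-5 itself.
- *That the bias is 0.08 to 0.20 SD.* Figures of that size follow if the criterion ranks participants exactly as the outcome does and a quarter to a half of those who stop short meet it. For example, with r = 1, q = 1/3 and s = 0.2, 0.2 × 0.3636 / 0.8667 = 0.084. Neither assumption suits criteria this strict.

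**Conclusion.** The point holds as a weakness of one sensitivity analysis. The therapy arms are selected on a post-randomisation proxy of CAPS-5, the selection differs by arm, and the comparator is presumably unselected. The textual part needs no assumption.

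The bias probably runs towards PE and EMDR against WL. Its size cannot be computed from the SAP. The illustration of about 0.02 to 0.14 SD, beside a planned effect of 0.5, rests on 20% to 40% stopping short independently of outcome, 10% to 30% meeting the criteria and a criterion-outcome correlation of 0.5 to 0.7. It is smaller if few meet the criteria. For CR the direction could be the reverse.

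The ITT primary analysis is unaffected, and the clinical early-completion rule is not in question. The change should be made because agreement between this analysis and ITT would carry little weight as evidence of robustness.

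**What to change.** In Sensitivity Analyses:

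1. State that all WL participants are retained.
2. Estimate the effect of receiving each therapy v WL as a complier-average causal effect, with randomisation as the instrument. Define receipt by one pre-set minimum session count common to CR, PE and EMDR, with no symptom criterion. Set the count low enough that early completers are classed as having received therapy. A single high count would class them as untreated although they may have benefited most, which breaks the assumption the method rests on.
3. Repeat with a second count.
4. If the completer analysis is kept, label it a non-randomised, descriptive comparison and do not cite it as evidence of robustness. Report early completers descriptively.

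The cost is a few lines of SAP text and a short instrumental-variable analysis on session counts, which the existing 16-session definition already requires. There are three downsides. The estimate assumes that attendance below the count has no effect. It is less precise than ITT. And with WL untreated until T6 it is essentially the ITT effect divided by the proportion reaching the count, so it largely shares its test with ITT. It answers what receiving therapy does and is not an independent check of the primary result.

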## Sample Size Calculation

A formal power analysis was conducted to determine the required sample size for the planned longitudinal intention-to-treat (ITT) analyses using linear mixed models (LMM).

Based on data from previous randomized controlled trials in this field , the calculation used the following parameters: significance level ( $\alpha$ ) of 0.05 (two-sided), power (1- $\beta$ ) of 0.80, expected correlation between repeated measures ( $\rho$ ) of 0.45, and 3 repeated follow-up assessments. The minimum detectable effect size was set at 0.5 (medium effect, compared to waiting list control), while accounting for an anticipated attrition rate of 20%. These calculations indicated that 50 participants would be needed in each study arm. Therefore, our aim will be to randomize a total of 200 participants.

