## **Statistical Methods**

## General principles

This Statistical Analysis Plan describes the methods for analysis of the effect of traumafocused therapies for individuals with PTSD and psychosis on primary, secondary, and adverse outcomes. Other analyses outlined in the published protocol, such as costeffectiveness analysis, will be described and published separately.

All analyses will be completed in R (version 4.4.2) unless stated otherwise. All tests are two-sided and a significance level of  $\alpha$ =0.05 is adopted.

Data will be analysed following the intention-to-treat principle, ensuring all randomized participants are analysed in their assigned groups, regardless of adherence or missing data. Missing data will be treated as missing at random.

Statistical analyses will be carried out by [name], under supervision of dr. [name], dr. [name], dr. [name], and prof. dr. [name]. An independent statistician will be consulted throughout the analysis process.

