## Primary Outcome Analysis

To evaluate changes in researcher-rated PTSD symptom severity over time and treatment differences, a LMM will be fitted using restricted maximum likelihood (REML) estimation. The primary model includes baseline scores as covariate, treatment condition as fixed effect, time as categorical variable, an interaction term between treatment condition and time, and a random intercept for each participant to account for within-subject correlations. An interaction effect between treatment condition and time variables would indicate differential treatment effects over time. To appropriately model the within-subject correlation of repeated outcome measures across unequally spaced timepoints, an unstructured covariance matrix will be applied to the residuals in the LMM. This results in the following model equation:

$$Y_{ij} = \beta_0 + \beta_1 \cdot Baseline_i + \sum_{k=1}^{3} \beta_{2k} \cdot Group_{ik} + \sum_{l=1}^{3} \beta_{3l} \cdot Time_{jl} + \sum_{k=1}^{3} \sum_{l=1}^{3} \beta_{4kl} \cdot (Group_{ik} \times Time_{jl}) + u_i + \varepsilon_{ij}$$

Where:

- *Yii*: Outcome for participant *i* at timepoint *j*
- *Baseline*i: Baseline outcome value for participant *i*
- *Groupik*: Dummy-coded treatment condition indicators (3 dummies: CR, PE, EMDR; WL = reference)
- *Timejl*: Dummy-coded time indicators (3 dummies: midtreatment, posttreatment, 6-month follow-up; baseline = reference)
- $Group_{ik} \times Time_{il}$ : Group-by-time interaction terms
- $u_i$ : Random intercept for participant i
- $\varepsilon_{ii}$ : Residual error
- Fixed effects:
  - Intercept  $\beta_0$ : Mean outcome at baseline for WL
  - $\circ$   $\beta_1$ : Effect of individual baseline outcome value (covariate)
  - $\circ$   $\beta_{2k}$ : Group main effects at baseline, compared to WL
  - $\circ$   $\beta_{3l}$ : Time effects for WL (how outcomes change over time within WL)
  - $\circ$   $\beta_{4kl}$ : Additional group-specific changes over time relative to WL

To quantify the magnitude of treatment effects, effect sizes will be estimated for timepoints T3 and T6 based on the mean pre-post change (i.e. baseline scores vs. follow-up scores) of the treatment condition minus the mean pre-post change of WL, divided by the pooled pretest standard deviation 

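### The SAP's comparison of assessment completers with multiple imputation cannot examine whether data are missing at random, and no planned analysis departs from that assumption

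*SAP*

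**What the plan says.** Under General principles the SAP sets the assumption for its analyses: "Missing data will be treated as missing at random". The same section states the intention-to-treat rule, "ensuring all randomized participants are analysed in their assigned groups, regardless of adherence or missing data". Under Primary Outcome Analysis, "a LMM will be fitted using restricted maximum likelihood (REML) estimation". A likelihood-based fit of this kind is valid under MAR when it uses all observed outcomes.

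The Sensitivity Analyses section opens with its aim: "To evaluate the robustness of the findings of the primary outcome analysis, the following sensitivity analyses will be performed". It then lists two analyses. One is per-protocol. The other will "compare primary model with only assessment completers to model with missing outcome data imputed to examine if data is missing at random (MAR"). The method follows: "Missing data in the outcome variable will be handled using multiple imputation via chained equations". The SAP does not define assessment completers, gives no rule for reading a difference or an agreement, and describes no analysis that departs from MAR.

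**The concern.** The SAP gives the comparison an inferential purpose that it cannot serve. Whether data are MAR or MNAR depends on the values that were not observed. Standard chained-equations imputation fills those values in under MAR, so it shares the assumption it is meant to check.

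Two misreadings are possible. If the fits agree, the report may say that MAR is supported when it is not. If they differ, it may say that MAR has failed when drop-out depended only on observed scores.

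The anticipated attrition is 20%, about 10 of 50 participants per arm. The per-protocol analysis restricts the sample to therapy completers and does not address the unseen outcomes of those who leave. The possibility that drop-outs do worse than the model predicts is therefore never tested.

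**Working it through.** **Inputs from the SAP (Sample Size Calculation).** Effect 0.5 SD against WL; correlation between repeated measures "of 0.45, and 3 repeated follow-up assessments"; attrition 20%; two-sided alpha 0.05; power 0.80; 50 per arm.

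**The plan's own figure.** For the mean of 3 correlated follow-ups the variance factor is (1 + 2 × 0.45)/3 = 0.6333. Then n = 2 × ((1.960 + 0.842)/0.5)² × 0.6333 = 39.8, rounded up to 40, and 40/0.80 = 50 per arm. This matches the SAP and is not in dispute. The same inputs are used below.

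**Assumptions that are not in the SAP.** These are the drop-out mechanisms, the 0.5 SD shift and compound symmetry. The contrast is one active arm against WL at T6, and negative values favour therapy. In large-sample simulations with 400,000 per arm, drop-outs lose T3 and T6, and imputation is by regression on T0 and T2 within arm.

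**A. MAR fails.** Drop-out is 20% at random in both arms, and active-arm drop-outs are 0.5 SD worse than predicted.
- Truth: -0.50 + 0.20 × 0.5 = -0.40.
- Completers: -0.50. Imputation: -0.50.
- The gap is zero, yet both overstate the effect by 0.10 SD, which is 0.10/0.40 = 25% of the true effect. Baseline adjustment does not change this.
- In general the hidden bias is attrition × shift: 0.20 × 0.25 = 0.05 SD, up to 0.20 × 1.0 = 0.20 SD.

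**B. MAR holds.** In the active arm, half of those in the worst 40% at T2 drop out. In WL, 20% drop out at random.
- The mean T2 deviation is 0.966 in the worst 40% and -0.644 in the other 60%. Among active completers it is (0.6 × (-0.644) + 0.2 × 0.966)/0.8 = -0.24.
- Carried to T6, this is 0.45 × (-0.24) = -0.11, so the unadjusted completer contrast is about -0.61.
- The plan's model adjusts for baseline, and baseline among completers is shifted by the same -0.11. With a completer slope near 0.44, the remaining bias is -0.11 × (1 - 0.44) = -0.06.
- Baseline-adjusted completers: -0.56. Imputation: -0.50. Truth: -0.50.
- The gap of 0.06 SD would invite the conclusion that MAR had failed, although it holds.

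**C. Mechanisms that do not mislead in this way.**
- The same T2-driven MAR drop-out in both arms: completers, imputation and truth are all -0.50. There is no gap, although the data are not MCAR.
- The same 0.5 SD shift and the same attrition in both arms: the shifts cancel, and all three are again -0.50.

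**Check at the trial's size.** This used 50 per arm, 1,500 simulated trials per mechanism, about 20% missing at T6, a true effect of -0.50, and stronger drop-out of opposite sign in the two arms.

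| Mechanism | Completers | Imputation | Trials with a gap above 0.1 SD |
|---|---|---|---|
| MCAR | -0.51 | -0.51 | 1% |
| MAR | -0.62 | -0.50 | 60% |
| MNAR | -0.82 | -0.82 | 2% |

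The largest bias, 0.32 SD under MNAR, comes with no average gap.

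**The two readings of the undefined term.** If assessment completers are participants with every assessment, both A and B can occur. If the phrase means the primary model fitted to all observed rows, that model and the imputation both rest on MAR and nearly agree by construction. B then disappears, and the check can only reassure.

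**The case against.** The strongest reply accepts that the wording is wrong but holds that little follows from it. Four arguments have force.

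First, a reader might infer that the comparison always gives the wrong verdict. The results under C show that it does not. The false alarm needs drop-out that differs between arms and the narrower reading of completers. The SAP also sets no decision rule, so any verdict is the reader's inference. *Can mislead* is as far as the evidence goes.

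Second, a reader might infer that the SAP contradicts its intention-to-treat rule by describing the primary model as fitted to completers only. The bullet sits among sensitivity analyses, where a restricted set is legitimate, and the phrase may simply mean non-imputed data. The document supports a charge of ambiguity, not of proven contradiction.

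Third, the 0.5 SD shift is invented for illustration and applied to one arm. The SAP gives no such figure, and equal shifts at equal attrition cancel. The 0.10 SD is not a forecast of bias in this trial.

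Fourth, the number and type of MNAR analyses are partly a matter of preference. That stands, and it is why one such analysis is enough.

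None of this rescues the stated purpose. On either reading, the comparison cannot distinguish MAR from MNAR.

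**Conclusion.** The concern holds in this form: the SAP misstates what the comparison can show, leaves its analysis set undefined, and plans no analysis that departs from MAR despite 20% anticipated attrition. The logical point needs no assumption about drop-out.

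The sizes do need assumptions. A hidden overstatement of 0.10 SD follows from an assumed 0.5 SD shift confined to active-arm drop-outs, and it scales with that shift. A spurious gap of 0.06 SD follows from T2-driven drop-out in the active arm only, and from reading completers as participants with every assessment. False reassurance is the more serious risk because it survives both readings.

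The primary estimate under its stated MAR assumption and the sample size are unaffected. The SAP should be corrected before analysis.

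**What to change.** Under Sensitivity Analyses and Primary Outcome Analysis:

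1. Delete the words claiming that the comparison examines MAR.
2. State that the primary model uses all available outcome rows from all randomised participants. If a fit restricted to participants with every assessment is kept, define that set and say that a difference from the imputed result indicates at most a departure from MCAR.
3. Describe the multiple imputation as an analysis made under MAR.
4. Add one prespecified MNAR analysis of the CAPS-5 contrasts on the same imputation engine: delta-adjusted imputation, with the shift varied by arm up to the tipping point and the range fixed in advance. Reference-based imputation, in which therapy-arm drop-outs follow the WL trajectory, is an acceptable alternative. Report each primary contrast under it.

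The cost is a few sentences in the SAP and modest extra programming on imputation that is already planned. No new data are needed.

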# Safety Analysis

During study participation, trial therapists were asked to monitor and report any severe adverse events (e.g., death, life threatening situations) and their possible study-relatedness. Severe adverse events will be summarized over the full study period (i.e., baseline up until 6-month follow-up) and reported by treatment arm.

In addition, all participants were asked to monitor adversities and revictimization weekly using smartphone questionnaires up to the 6-month assessment timepoint to enhance ecological validity. To assess group differences on these tertiary outcomes, events reported in the weekly online questionnaires will be aggregated between assessment timepoints and averaged to generate a single composite score corresponding to each formal assessment timepoint (i.e. baseline, T2, T3, and T6) for LMM-analysis.

<sup>a Early completion of EMDR or PE therapy was permitted only after consultation with the therapist and supervisor, and required that all trauma memories on the case conceptualization achieved Subjective Units of Distress (SUDs) scores of 0, participants scored 0 on both the re-experiencing (section B) and avoidance (section C) sections of the PCL-5, all psychosis targets achieved SUD scores of 0, and psychosis symptoms were in remission.

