# Randomisation and Blinding

Participants are randomized by an independent researcher using a randomization programme (http://www.randomizer.org) with a 1:1:1:1 allocation ratio, stratified by trial therapist. The allocation sequence is saved in a protected folder to which the research team has no access. The independent researcher informs the therapist of the allocation who in turn informs the participant.

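### Severe adverse events are tabulated by arm from reports of unblinded trial therapists, whose planned therapy contact differs between the therapy arms and the waitlist, so capture may depend on arm

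*SAP*

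**What the plan says.** **Source and relatedness.** The SAP, Safety Analysis, states that "trial therapists were asked to monitor and report any severe adverse events". The same sentence gives examples of such events and adds relatedness to the therapists' task: "e.g., death, life threatening situations) and their possible study-relatedness". No other reporter of severe events is named.

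**Presentation.** These events are to be "summarized over the full study period (i.e., baseline up until 6-month follow-up) and reported by treatment arm". No test, ratio or model is planned for them.

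**Contact.** Study Design says: "Therapy in all three active arms will be delivered over 16 sessions by trained therapists working in routine mental health services". For the waitlist (WL) it says: "Participants in the WL condition receive therapy of choice after T6". The Introduction places posttreatment (T3) at 3 months and the last follow-up (T6) at 6 months.

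**Allocation.** Under Randomisation and Blinding, participants are randomised "with a 1:1:1:1 allocation ratio, stratified by trial therapist", and "The independent researcher informs the therapist of the allocation who in turn informs the participant".

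**A source common to all arms.** Safety Analysis also says that "all participants were asked to monitor adversities and revictimization weekly using smartphone questionnaires up to the 6-month assessment timepoint". These reports are averaged into one score per assessment for a linear mixed model. No step is stated that takes a severe event found there into the severe-event summary.

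**The concern.** The only named reporter is someone whose planned contact with the participant depends on the arm, and the arm is what the table displays. An event is more likely to become known to a therapist who sees the participant over 16 sessions than to one whose planned therapy with that participant begins only when the safety window has closed. Therapists also know the allocation, and relatedness to a therapy cannot be judged in the same way in an arm that has not received one.

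At stake is how the severe-event table can be read. If WL events are captured less completely, equal true risk looks like harm from trauma-focused therapy, and a true reduction against WL can be hidden. A low WL count could not be told apart from a low rate of detection. The three therapies have the same planned contact, so the problem lies between them and WL.

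**Working it through.** The plan gives no severe-event rate and no capture rate, so it has no figure of its own to reproduce here. The check is a reading of the sections side by side, followed by an illustration on assumed rates.

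**Step 1. What the SAP fixes for each arm**

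| Feature | CR, PE, EMDR | WL | SAP section |
|---|---|---|---|
| Named reporter of severe events | trial therapist | trial therapist | Safety Analysis |
| Reporter knows the allocation | yes | yes | Randomisation and Blinding |
| Planned therapy, T0 to T3 | 16 sessions (early completion possible in EMDR and PE) | none | Study Design; Safety Analysis footnote |
| Planned therapy, T3 to T6 | none stated | none | Introduction; Study Design |
| Safety window | T0 to T6 | T0 to T6 | Safety Analysis |
| Weekly questionnaires to 6 months | yes | yes | Safety Analysis |
| Usual care and the T0, T2, T3 and T6 assessments | yes | yes | Study Design |

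The arms differ in one row only, the planned therapy from T0 to T3, which is the first half of the window.

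**Step 2. Effect on an apparent risk ratio**

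Let a be the proportion of events captured in a therapy arm and c the proportion captured in WL. Then

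apparent ratio = true ratio × a / c.

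*Assumption set A: capture constant over the 6 months, a = 0.95, true ratio 1.*

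| c | a / c |
|---|---|
| 0.95 | 1.00 |
| 0.80 | 1.19 |
| 0.60 | 1.58 |
| 0.40 | 2.375 |

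*Assumption set B: 0.90 captured in the therapy arms while sessions run (T0 to T3), WL-level capture afterwards, and events spread evenly.* Each period is 3 of the 6 months, so a = (0.90 + c)/2.

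| c | a | Apparent ratio, true ratio 1.0 | Apparent ratio, true ratio 0.5 |
|---|---|---|---|
| 0.90 | 0.90 | 1.00 | 0.50 |
| 0.70 | 0.80 | 1.14 | 0.57 |
| 0.50 | 0.70 | 1.40 | 0.70 |
| 0.30 | 0.60 | 2.00 | 1.00 |

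The first row of each table is the case of equal capture, in which the distortion vanishes.

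**Step 3. Scale in counts**

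The SAP's Sample Size Calculation gives 50 per arm. Assume a true risk of 10% in every arm, or 50 × 0.10 = 5 events. Under set A a therapy arm reports 5 × 0.95 = 4.75 on average. WL reports 4.75, 4.00, 3.00 or 2.00 for c = 0.95, 0.80, 0.60 or 0.40. The largest gap is 4.75 − 2.00 = 2.75 events, so a few missed WL events would change how the table looks.

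**The case against.** The strongest case against the point has five parts.

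- **No formal comparison is planned.** Severe events are summarised and reported by arm. Group differences are to be assessed only on the weekly questionnaires, which every arm completes. A reader might infer that the SAP plans to compare severe-event rates between arms, and it does not. This stands, although a by-arm table that includes WL still invites the comparison.
- **Absence of contact with WL participants is not stated.** One might infer that therapists do not see them before T6. The SAP supports this for planned therapy sessions only. Randomisation is stratified by therapist, and the therapist tells each participant the allocation, so WL participants have a linked therapist and at least that contact. The SAP puts no arm limit on the duty to monitor. This stands.
- **Silence is not a rule.** Naming one source does not exclude others, and collection procedures may be in the protocol, which is not shown. This stands in part. The SAP itself sets out the source, window and layout of the table, and as set out they leave capture in WL open.
- **Capture rates are assumed.** Deaths and life-threatening events are among those most likely to surface through usual care or missed assessments in any arm. This stands, and low WL capture in particular has no support in the documents.
- **The remedy has limits.** The weekly items are not shown, a death cannot be self-reported, and assessment or usual-care records are not shown to hold severe events. This stands and limits the fix to records that exist.

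Therapists' knowledge of allocation is inherent in a psychotherapy trial and is no fault in itself.

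**Conclusion.** The by-arm severe-event summary is at risk of differential ascertainment between the three therapy arms and WL. The risk rests on three facts in the SAP: trial therapists are the only named reporters, they know the allocation, and their planned therapy contact from T0 to T3 is 16 sessions in CR, PE and EMDR against none in WL. It does not extend to contrasts among the three therapies, and it lies mainly in T0 to T3.

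The size cannot be derived. Apparent ratios of 1.0 to about 2.4 at equal true risk are illustrations that depend wholly on the assumed capture rates. The effect is zero if WL events were captured equally well. It would be tempting to conclude that the safety table is biased against therapy. The documents do not show this, because they neither give capture rates nor rule out other routes by which WL events become known.

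What remains is a low-cost improvement: the trial has a source common to all four arms that can partly check the therapist reports, and the SAP states no such use of it.

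**What to change.** In the SAP's Safety Analysis:

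1. State how severe events in WL participants were captured before T6.
2. Screen the weekly questionnaire reports of all four arms, up to 6 months, for events that meet the severe-event definition. Add assessment-visit or usual-care records only where these exist. Reconcile all of them with the therapist reports.
3. Tabulate by arm the number of participants with at least one all-cause severe event and the number of events, each flagged by source and by period (T0 to T3, T3 to T6).
4. Present therapist-rated relatedness descriptively, without contrast to WL.

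The cost is a change of wording and a one-off data review, with no new data collection. Some self-reported events will be too vague to classify. Non-response to the weekly questionnaires may itself depend on arm, so the reconciled table would reduce unequal capture without guaranteeing equality.
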